#### Guideline recommended antenatal care

- Anatomy scan (between 18-22 weeks' gestation) [Medicaid claims data]
- Gestational diabetes test (between 24-28 weeks' gestation) [Medicaid claims data]
- TDAP vaccine (between 27-36 weeks' gestation) [Medicaid claims data]
- Group B strep test (between 35-38 weeks' gestation) [Medicaid claims data]

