4.4. List inclusion criteria

Eligibility Criteria	Process for assessing criteria
Female	Applicant's self-report
No previous live births	Applicant's self-report
Currently pregnant	Applicant's self-report of having received a positive pregnancy test
Gestation period less than 28 weeks (i.e. less than or equal to 27 weeks, 6 days)	Estimated due date; best guess of practitioner and applicant
Ages 15-55	Applicant's self-reported date of birth
Income level meets Medicaid eligibility criteria	Applicant's self-report, verify enrollment and/or eligibility in QuickChecks (State eligibility determination program)
Live within an area serviced by a NFP Implementing Agency	Applicant's self-report of current mailing address
Not currently enrolled in the study	Search for matches by last name & DOB in the study database
Not incarcerated or living in lock down facilities	Applicant's self-report or as reported by the relevant agency or facility

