applicant will be informed during the consent process that the interview may also be recorded for quality assurance purposes.

All eligible program applicants who provide their written consent and complete the baseline interview will be randomly assigned “on-the-spot” to a treatment group that is offered access to the NFP program or to a control group that is not offered the opportunity to enroll in NFP. Program staff will use a pre-programmed randomization function on their tablets to conduct the random assignment. Program staff will explain to the participant that the computer chooses which study group she will be assigned to, and that her assignment is not dependent on any personal traits or characteristics.

If the applicant is assigned to the control group, the program staff will explain that she was not chosen by the computer to receive NFP services, but that she may continue to seek care at the health care center as she normally would. The program staff will also provide a list of other resources and programs that are available in the community.

If the applicant is assigned to the treatment group, the program staff will proceed to schedule her first home-visiting appointment. The program staff will also provide treatment group members with a list of other resources and programs that are available in the community. In response to COVID-19, the materials the applicant would have otherwise received in person (copy of the consent form, \$25 gift card, and list of community resources) will be mailed to the address the applicant provides.

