covering the weeks of gestation provided in the obstetric estimate on the vital record until the date of birth or fetal death. In the absence of an index birth or fetal death, we define the pregnancy period as the period covering 42 weeks prior to the expected delivery date provided on the baseline survey. We will consider a mother to be matched to the index pregnancy if she has any matched administrative records pertaining to the index pregnancy (including antenatal care, probable pregnancy loss or birth related records from Medicaid claims or hospital discharge or evidence of a birth or fetal death from vital records). Table 1 summarizes the definitions and data sources used to identify index pregnancies and live index births.

When tracking children in the study, we will define two key periods. We anticipate that the children of most mothers who enroll in the trial will be eligible for Medicaid for their entire first year of life, as the income requirements for infants are similar to those of pregnant women. However, as summarized in Table 2, in some years of the study, income requirements became more restrictive after the first year of the child's life. Furthermore, families whose children remain income-eligible into their child's second year of life must submit an annual review form to retain coverage. Therefore, we plan to measure outcomes for children resulting from index births in the study to two critical time points: through their first 12 months of life and through their first 24 months of life.

Table 1. Sample Tracking Definitions

Sample tracking measure	Data Source(s)	Definition
Index pregnancy	Birth Certificates, fetal death records, Medicaid claims and eligibility, hospital discharge	Having matched administrative records for one or more of the outcomes listed below during the period of the index pregnancy. This period is defined as covering the weeks of gestation provided in the obstetric estimate on the vital record until the date of birth or fetal death, when a mother has a matched index birth or fetal death record. In the absence of an index birth or fetal death, we define the pregnancy period as the time covering 42 weeks prior to the expected delivery date provided on the baseline survey.

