## **B. Analytical considerations**

### **B.1. Control variables**

In addition to reporting unadjusted models of program impact, we plan to report models that adjust for characteristics at baseline that may be associated with our primary academic outcomes. These include participant age, race and ethnicity, gestational age at study enrollment, relationship with the father of the child, education, employment, use of social services, housing stability, health care utilization, health behaviors and physical and mental health status all measured during the baseline survey. Specific variable definitions that we plan to include as control variables are specified below. Binary variables will be coded as "1", "0", or missing; for coding categorical variables, we will consider distributions across the control and treatment groups including missing values. We plan to use the same set of control variables in all analyses.

- Implementing Agency

- Indicators for each implementing agency enrolling study participants
- Demographics:
  - Indicator for age equal to 15, 16, or 17
  - Indicator for age equal to or greater than 28
  - Race – indicators for non-Hispanic Black, non-Hispanic white, other
  - Ethnicity – indicator for Hispanic/Latina
- Gestational age at time of study enrollment
  - A continuous variable of weeks to delivery as calculated by difference in estimated due date and the survey date
- Relationship with father of the child
  - Indicator for daily interaction with father of the child
- Education
  - Indicator for high school diploma or GED with no higher education
  - Indicator for less than high school diploma
- Employment, Income, and Financial Resources
  - Indicator for whether the mother is working for pay at the time of the survey
- Social services
  - Indicator for receiving one or more social service (i.e. TANF, SNAP, SSI, unemployment benefits, and WIC)
- Housing stability
  - Indicator for moving two or more times in the previous twelve months
  - Indicator for living with parents
- Access and utilization of health care, including mental health and maternal health
  - Indicator for receiving at least one antenatal care visit before time of survey
  - Indicator for having obtained care at a hospital ER in past six months
  - Indicator for receiving mental health treatment in the previous year
- Health behavior (e.g. drinking and smoking)
  - Indicator for reporting having consumed alcohol in the three months before pregnancy

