### Utilization of health care services during pregnancy

- Adequacy of Prenatal Care Utilization Index (APNCU) [vital records data]
- Number of emergency department visits during pregnancy [all-payer hospital discharge data]
  - To better understand the effect of NFP on emergency department utilization, we may also examine treatment vs. control differences in emergency department use by trimester of the emergency department visit and by the enrollee's overall adequacy of prenatal care (APNCU).
- Number of ultrasounds during pregnancy [Medicaid claims data]

- Consultation with maternal fetal medicine specialist [all-payer hospital discharge data]
- Dental visit during pregnancy [Medicaid claims data]

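### The 18-22 week anatomy-scan outcome includes women randomised after its window has closed, which shrinks the measurable effect although the ITT contrast stays valid

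*SAP*

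**What the plan says.** Protocol 4.4 sets the enrolment limit: "Gestation period less than 28 weeks (i.e. less than or equal to 27 weeks, 6 days". Assignment happens at the enrolment visit, straight after the baseline interview (Protocol 4.6): "Program staff will use a pre-programmed randomization function on their tablets to conduct the random assignment".

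SAP Addendum 1, under guideline recommended antenatal care, lists an item beginning "Anatomy scan (between 18-22" (weeks of gestation, from Medicaid claims) and "Gestational diabetes test (between 24-28 weeks' gestation) [Medicaid claims data", together with Tdap vaccination (27-36 weeks) and a Group B strep test (35-38 weeks). The section that follows dates each test by gestational age alone. Its one gestation-based restriction is that the pregnancy lasted to the recommended age. Nothing there refers to gestation at randomisation.

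Section 1.7 combines the four services into an index equal to the proportion received. Addendum 4, Table 4, carries the anatomy scan into the prenatal outcomes as one of ten items.

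Other outcomes, such as "Number of emergency department visits during pregnancy", run over the index pregnancy, which section A.1 defines as "covering the weeks of gestation provided in the obstetric estimate on the vital record until the date of birth or fetal death". That period starts before randomisation.

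Section B.1 adjusts for gestation at enrolment: "A continuous variable of weeks to delivery as calculated by difference in estimated due date and the survey date". It also adjusts for any antenatal visit before the survey, emergency care in the past six months and mental health treatment in the past year. ED use by trimester is an optional extra analysis.

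**The concern.** The scan window can close about five weeks before the last date on which a woman may be randomised. From 23w0d onward her scan status is a baseline fact, and the programme's effect on it is zero by construction. Including such women averages a real effect with zeros.

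The SAP already applies risk-set reasoning at the far end of pregnancy, by dropping women who delivered before a service was due. It does not apply it at the near end, where the relevant variable is measured before randomisation and is already held.

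At stake is a true improvement in scan uptake being read as little or no effect, with some of that carried into the four-service index. In Addendum 4, the full covariate set uses all baseline information. If gestation at enrolment is included, late enrolees could look like women who benefit less partly because the window had already closed.

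**Working it through.** **No plan figure to reproduce.** Protocol 5.2 gives power only for the primary outcomes; no control rate, effect size or power is stated for any antenatal-care outcome. As a calibration, the two-proportion method used below was run on birth spacing: 2,000 controls, 4,000 treated, control rate 0.14, difference 0.14 x 0.18 x (0.95 - 0.05) = 0.0227. It returns 70.3%, against the stated figure of roughly 70%.

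**Inputs from the documents.** Latest randomisation 27w6d; scan window 18-22 weeks, read here as ending at 22w6d; two-sided alpha 0.05; 3,295 and 1,637 mothers with an index birth (Addendum 4, Table 3). Claims-based outcomes will use fewer, because mothers unmatched to Medicaid are left out.

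**Not in the documents.** The distribution of gestation at enrolment, hence f, and the control rate. Both are assumed, with ranges.

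**Dilution.** Let d be the average effect in women randomised before the window closes.

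- Full sample: effect (1-f)d, standard error proportional to 1/sqrt(N).
- Restricted sample: effect d, standard error proportional to 1/sqrt((1-f)N).
- z(restricted)/z(full) = 1/sqrt(1-f).

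Because d averages over women randomised inside the window, the ratio holds whatever share of the effect they retain. It assumes similar outcome variance and arm ratio in early and late enrolees.

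| f | Gain in z from restricting | Full-sample power if restricted power is 80% | Power as planned / restricted, with d set to give 80% if f were 0 |
|---|---|---|---|
| 10% | 5% | 76% | 71% / 76% |
| 20% | 12% | 71% | 61% / 71% |
| 30% | 20% | 65% | 50% / 65% |
| 40% | 29% | 58% | 39% / 58% |

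The last column uses 3,295 v 1,637. Assumed control rates of 40%, 60% and 80% give nearly the same results. At 60% and f = 30%, the smallest effect in still-reachable women detectable with 80% power is 5.9 points as planned and 4.9 points restricted.

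**Plausible f.** With uniform enrolment from 6w0d to 27w6d (assumption), f = (28 - 23)/(28 - 6) = 5/22 = 23%, and the gain in z is 1/sqrt(0.773) = 1.14. Starting at 12w0d instead, f = 5/16 = 31%.

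**Where to cut.** The restriction must use the window's close, not its opening. On the same uniform assumption, keeping only women randomised before 18w0d drops 10/22 = 45%. If women randomised inside the window keep their full effect, z is proportional to sqrt(0.545) = 0.739, against 0.773 for the full sample, so that cut loses power.

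**Other timed services.** The diabetes window runs to 28 weeks, Tdap to 36 and Group B strep to 38. None has closed by 27w6d.

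**Index.** The scan is one service of four. If all four effects were equal (assumption), the index effect is multiplied by (4 - f)/4: 0.975 at f = 10% and 0.925 at f = 30%.

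**Counts.** Events before randomisation add the same expected number to both arms. The absolute mean difference in ED visits or ultrasounds is therefore unchanged; the variance rises and the relative effect shrinks.

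**The case against.** The strongest reply is that ITT among all enrolees is a legitimate estimand, estimated without bias, and that the effect in earlier enrolees is a different question. That stands as regards validity: events before randomisation balance in expectation. A reader might infer that the planned scan analysis is biased or invalid; the documents do not support that. They show an effect averaged over women in whom it must be zero.

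A reader might also infer that every outcome measured during pregnancy is pulled toward zero. For absolute differences in counts that is wrong, as shown above. Yes/no outcomes over the whole pregnancy, such as a dental visit, are different again. A woman with an earlier event is already counted, but counting only later events would code women already served as unserved. The documents do not allow that loss to be sized, and no change is proposed for them.

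The section B.1 covariates and the optional trimester analysis are real mitigation. They can recover precision, and for ED use they go some way. A main-effect covariate cannot restore a diluted absolute effect on the scan.

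Uniform enrolment may overstate f, since Protocol 2.1 says visits begin as early in pregnancy as possible. The SAP also refers other methods to a published protocol that is not among these documents, so a rule there cannot be excluded.

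Finally, Addendum 4 (February 2025) describes the trial manuscripts, prenatal outcomes among them, as published or forthcoming. Replacing a main analysis after results are known would be a post hoc change. That limits how the remedy should be applied, not whether the dilution exists.

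**Conclusion.** The point holds for the anatomy scan and for the two indices that include it. Women randomised from 23w0d contribute a zero effect by construction, and nothing in the protocol or SAP removes them. The loss is of sensitivity: the ITT effect is (1-f) of the effect in women who can still be affected, and restricting at the window's close raises z by 1/sqrt(1-f). That is 5-29% for f of 10-40%, and about 14% at the illustrative f of 23%. The size rests on an enrolment distribution the documents do not give; the direction does not.

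For ED visits and ultrasounds the issue is smaller: added variance and a reduced relative effect. The outcomes concerned are secondary or exploratory, and the three primary outcomes are untouched.

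**What to change.** - **Anatomy scan.** Analyse it in women whose gestation at randomisation, from the baseline due date, is under 23w0d, and report the full-sample ITT alongside. This is a restriction on a pre-randomisation variable, so it introduces no selection by arm. State whether week 22 runs to 22w6d.
- **Four-service index.** For each woman, use the services whose window had not closed at randomisation. In practice the scan leaves the denominator for women randomised at 23w0d or later.
- **Diabetes test, Tdap, Group B strep.** Leave the samples unchanged.
- **ED visits and ultrasounds.** Count from the randomisation date, adjust for or offset by weeks to delivery (already a covariate) because follow-up time then differs between women, and keep whole-pregnancy counts as secondary.
- **Timing.** Where results are already reported, add these as labelled sensitivity analyses. Apply them in Addendum 4, whose analyses had not been run when it was submitted.
- **Report** the distribution of gestation at randomisation by arm, so that f is known.

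The cost is SAP wording and a date filter on data already held. The downsides are a smaller sample for the scan, an effect that applies only to women enrolled before 23 weeks, and some misclassification, because baseline gestation is an estimate by practitioner and applicant while test dates are placed using the vital-record obstetric estimate.

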#### Antenatal health

- Smoking cessation during pregnancy [vital records data]
  - We will consider an enrollee to have ceased smoking during pregnancy if their vital record indicates that they smoked pre-pregnancy and that they did not smoke during pregnancy.
- Recommended gestational weight gain [vital records data]
  - Gestational weight gain will be classified as “recommended” if it is within the guidelines published by the National Academy of Medicine (formerly the Institute of Medicine).

The guideline-recommended antenatal care services should be received at the appropriate gestational age during the pregnancy. The gestational age at the time of the test will be calculated as the date of the test minus the approximate date of last menstrual period (in days). We will approximate the enrollee's date of last menstrual period using the child's date of birth and obstetrician's estimate of gestational age at delivery from the vital records. If these fields are missing, we will define the approximate date of last menstrual period as the beginning date of the index pregnancy (defined above).

Each of these outcomes can only be measured among pregnancies that reach the gestational age at which the care is recommended. The main analyses will only include pregnancies that last at least as long as the gestational age recommended for each outcome. However, it is possible that NFP has a direct effect on gestational age, which would mean that the sample of mothers observed could differ across treatment and control arms. If that is the case (i.e., if gestational age at birth between treatment and control group is statistically significantly different), then we will conduct a bounding exercise as a robustness check for the guideline-concordant care outcomes. Using Group B Strep as an example, the main analysis will compute the average treatment effect (ATE) among people whose pregnancies last at least 35 weeks. If gestational age is statistically significantly different between control and treatment arms, we will estimate two bounds on this ATE: (1) a recalculated ATE assuming *all* people who

did not reach 35 weeks' gestation would have received the test, and (2) a recalculated ATE assuming *none* of the people who did not reach 35 weeks' gestation would have received the test.

Table 1.3. Codes for analyses of antenatal care utilization and quality

	CPT/HCPCS	NDC	ICD-10
Dental visit	D1110, D0120, D0140, D0150, D0160, D0170, D0191, D1206, D1208, D02*, D0330, D0340, D0350, D2391, D2392, D2393, D1351, D71*, D7210, D7220, D7230, D7240, D7241, D7250		
Ultrasound	76801, 76805, 76811, 76813, 76815, 76816, 76817, 76818, 76819, 76810, 76812		
Anatomy scan ultrasound (18-22 weeks)	76805, 76811, 76815, 76816, 76817, 76810, 76812		
Gestational diabetes test (24-28 weeks)	82950, 82951, 82947		
TDAP vaccine (27-36 weeks)	90696, 90697, 90698, 90700, 90701, 90714, 90715, 90471, 90472, 90460, 90461	49281040010, 49281040015, 49281040020, 58160084211, 58160084252	
Group B streptococcus test (35-38 weeks)	87150, 3294F, 87802, 87653, 87801, 87081, 87084, 87070, 87077, 87147		Z36.85

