  - Indicator for reporting having smoked cigarettes in the three months before pregnancy
- Psychological state/resources (measured on a PHQ-2 scale)
  - Indicator for PHQ-2 score of 3 or higher.
- Baseline measure of self-reported health
  - Indicator for self-reported health described as fair or poor.
- Maternal perceived stress level
  - Indicator for PSS-4 score of 4 or higher.
- Self-reported pregnancy risk factors

- Indicator for pre-pregnancy weight and height yielding BMI of normal.
- Family planning
  - Indicator for responding yes to having access to a place for family planning or birth control
  - Indicator for responding yes to wanting more children one day

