### Antenatal Care Utilization & Quality

Analyses of outcomes related to antenatal care utilization and quality is planned as a stand-alone analysis. We will examine three groups of outcomes related to antenatal care utilization and quality: utilization of health care services during pregnancy, guideline-recommended antenatal care, and indicators related to antenatal health. We list the outcomes that fall under each area, and their associated data sources, below. We also include the CPT/HCPCS, NDC (National Drug Code) and ICD-10 codes used to identify the outcomes that use Medicaid claims or hospital discharge data in Table 1.3.

The primary sample for this analysis will be mothers with an index birth. We will use vital records, hospital discharge, and Medicaid claims data for the analyses. Mothers who do not match to one of these data sources will not be included in the sample for the corresponding outcomes (e.g., mothers who do not match to Medicaid claims will not be included in the analyses of guideline-recommended antenatal care).

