**Table 2. Social Risk Factors**

	Definition	Sources
All observable risk factors	See Table 1	See Table 1
Recent arrest	Reported being arrested in the year prior to the survey date	Darling et al., 2024
High stress	Scored 9 or higher on PSS4	Darling et al., 2024 (mental health challenges); Stamuli et al., 2015 (mental illness). 9+ for moderate or severe perceived stress cutoff obtained from Eick et al., 2022
Depression	Scored 3 or higher on PHQ2	Darling et al., 2024 (mental health challenges); Kristensen et al., 2017 (uses the Edinburgh Postnatal Depression Scale (EPDS)); Stamuli et al., 2015 (mental illness)
Housing insecurity	Moved 2+ times in the previous year or if they reported not living in a private residence (dorm room, homeless shelter)	Darling et al., 2024; Catherine et al., 2020
Substance use	Reported either: 1) any smoking in the 3 months before or during	Darling et al., 2024; Stamuli et al., 2015

	pregnancy, or 2) more than 7 drinks per week on average in the 3 months before pregnancy	
Low social support	Responded "yes" to the following social support questions 0-2 times: "Someone to loan \$50", "Someone to help you if you were sick and needed to be in bed", "Someone to drive you to clinic or doctor if you needed a ride", "Someone to talk with about your problems"	Darling et al., 2024; Stamuli et al., 2015 (isolated)
Not fluent in English	Reported not speaking English very well or not at all	Darling et al., 2024 (migrant)
Limited access to healthcare	Reported not having a place for general healthcare if sick or needs advice about health, AND reported obtaining care at a hospital ER in the 6 months prior to the survey	Darling et al., 2024 (health human resource issues; lack of providers); Cavallaro et al., 2022 (unplanned hospital admission 2y prior to 20w gestation)
Do not have a driver's license	Does not have their own driver's license	Rice et al., 2024; Bellerose et al., 2022
Low financial independence	Respondent reported having neither their own bank account nor access to their own credit card	Stevens et al., 2024
Fair/poor health	Health self-reported as fair or poor before pregnancy	Price et al., 2017
Limited relationship with child's father	Does not see or talk to the father of the child daily	Darling et al., 2024 (unmarried); Tereno et al., 2022 (declares intention to raise child without the father); Foulon et al., 2015 (being a single parent or unmarried); Stamuli et al., 2015 (not married)

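### The smoking-cessation outcome, as worded, scores women who quit after enrolment as not having quit, so it can respond to NFP only through relapse prevention

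*SAP*

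**What the plan says.** SAP Addendum 1, in the stand-alone analysis of antenatal care, lists under Antenatal health the outcome "Smoking cessation during pregnancy [vital records data". A woman meets it when "their vital record indicates that they smoked pre-pregnancy and that they did not smoke during pregnancy". The section names no vital-record field and no trimester. It gives no end-of-pregnancy window and no alternative definition for women still smoking at enrolment. The analysis population is given ("The primary sample for this analysis will be mothers with an index birth"), but the SAP does not say whether the denominator for this outcome is all of those women or only the pre-pregnancy smokers among them.

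The timing comes from the Protocol. Section 4.4 requires a current pregnancy, assessed by "Applicant's self-report of having received a positive pregnancy test", and sets the upper limit as "Gestation period less than 28 weeks (i.e. less than or equal to 27 weeks, 6 days". Section 4.6 places the start of the programme after assignment: "If the applicant is assigned to the treatment group, the program staff will proceed to schedule her first home-visiting appointment".

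Two other SAP entries concern smoking. The only smoking covariate in section B.1 is "Indicator for reporting having smoked cigarettes in the three months before pregnancy". The substance-use risk factor in Addendum 4, Table 2, uses baseline reports of "any smoking in the 3 months before or during" pregnancy, so the survey appears to have asked about smoking after conception as well.

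**The concern.** The outcome is named for stopping during pregnancy, but its second condition is breached by any smoking after conception. For a woman who smoked in early pregnancy, that breach happens before she is randomised, and nothing she does afterwards can undo it. The behaviour a home-visiting nurse would most directly try to change, stopping from enrolment onward, is scored as failure in both arms.

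At stake is how a null result would be read. A small or absent difference could be reported as evidence that NFP does not help smokers quit, when most of what the measure records was settled before the programme began.

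**Working it through.** The documents give no cessation rate, expected effect, sample size or power for this outcome, so there is no planned figure to reproduce. The main step is logical and the arithmetic is illustrative.

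**Step 1. Apply the rule to each type of pre-pregnancy smoker**, assuming the record is accurate and the rule is read literally.

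| Smoking between conception and enrolment | After enrolment | Score |
|---|---|---|
| None | Stays abstinent | Ceased |
| None | Relapses | Not ceased |
| Some, stopped before enrolment | Stays abstinent or relapses | Not ceased |
| Still smoking at enrolment | Quits and stays abstinent | Not ceased |
| Still smoking at enrolment | Continues | Not ceased |

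Only the first two rows depend on what happens after randomisation. In the last three the score is fixed beforehand and is the same in both arms, so these women add exactly 0 to the intention-to-treat difference, which is the primary specification under SAP section B.3. No numerical assumption is needed.

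**Step 2. Size of the missed difference.** Let s be the share of pre-pregnancy smokers still smoking at enrolment and d the gain in their later quit rate due to NFP. Both are assumed: s from 0.30 to 0.70, d from 0.05 to 0.15. The control quit rate after enrolment is assumed to be 0.20, and the remaining women are taken as abstinent throughout.

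- As worded: each arm scores 1 − s, so the difference is 0.
- Scored late in pregnancy: control = (1 − s) + 0.20s and NFP = (1 − s) + (0.20 + d)s, so the difference is s × d.
- Lowest: 0.30 × 0.05 = 0.015, or 1.5 points (76.0% vs 77.5%).
- Middle: 0.50 × 0.10 = 0.05, or 5 points (60% vs 65%).
- Highest: 0.70 × 0.15 = 0.105, or 10.5 points (44.0% vs 54.5%).

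**Step 3. Would a late-pregnancy definition detect such differences?** Addendum 4, Table 3, gives substance-use counts of 823/3295 (NFP) and 441/1637 (usual care). These are a rough stand-in for the number of pre-pregnancy smokers, because they include women counted for heavy drinking and women who smoked only in pregnancy. With 823 vs 441 women, a two-sided test of two proportions at 0.05 has power of about 9% in the lowest case, 42% in the middle case and 95% in the highest.

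**Step 4. The route that remains open.** Suppose half of pre-pregnancy smokers were abstinent since conception and relapse is 30% in control and 20% under NFP (all assumed). The outcome as worded then gives 0.5 × 0.70 = 35% vs 0.5 × 0.80 = 40%, a 5-point difference. The measure is not inert, but what it picks up is relapse prevention.

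**The case against.** A reader might infer that the outcome cannot register any effect of NFP, or that the effect on it must be zero. The documents do not support that. Step 4 shows that NFP could move it by preventing relapse among women abstinent since conception. The zero applies only to women who smoked after conception. Nor does anything suggest a bias in favour of NFP.

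The SAP also does not say how the vital record holds smoking. If it is recorded by period, the analysts may have intended a late period, and the problem would disappear once that was written down. If the record holds a single yes/no for the whole pregnancy, the present definition may be the only one available. This objection is fair about the remedy. It does not rescue the text: another analyst following it would code any smoking in pregnancy as failure. The same section sets gestational windows and bounds for the guideline-care outcomes and offers nothing comparable for smoking.

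The sizes in Step 2 rest on assumed inputs, and a repaired outcome could still miss a real effect, with power of about 42% in the middle case. Both points stand.

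The consequence is also limited. This is one antenatal-health item and no part of any primary outcome. It is absent from Addendum 4, Table 4, which lists its neighbour, recommended gestational weight gain. That does not show the outcome was dropped, but it makes heavy reliance on it less likely. Finally, Addendum 4 (February 2025) counts prenatal outcomes among papers published or forthcoming, so replacing a definition dated January 2021 could be a change made after results were seen. That bears on how the fix is labelled.

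**Conclusion.** The concern holds for quitting after enrolment. Applied literally, the rule scores a woman who smoked between conception and enrolment as not having ceased, whatever she does afterwards. Her quitting adds 0 to the treatment difference, and the outcome is biased toward no effect on cessation. It stays open to NFP only through relapse prevention among women abstinent since conception.

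The zero contribution needs only the stated rule, an accurate record and enrolment during pregnancy. The 1.5 to 10.5 points among pre-pregnancy smokers is an illustration, not an estimate from the trial. The finding would fall away if the analysts meant a late-pregnancy field, but the SAP does not say so. It is worth correcting before this outcome is interpreted, and it leaves the trial's primary conclusions untouched.

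**What to change.** - Name the vital-record smoking field and the period it covers, and state the denominator as pre-pregnancy smokers.
- If the record holds smoking by period, define cessation as not smoking in the latest period of pregnancy it reports.
- Report the existing version, no smoking at any time in pregnancy, alongside. If arm comparisons have already been seen, label the new definition as an added or post hoc analysis.
- If the baseline survey permits, also report the effect among women smoking at enrolment.
- If the record has no period detail, rename the outcome as no smoking at any time in pregnancy, and state that a null result does not show that NFP fails to help smokers quit after enrolment.

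The cost is SAP text and one recoded variable from records the study already plans to use. If results have been seen, the cost also includes reporting the new analysis as post hoc. The downside is more reliance on accurate recording of one late-pregnancy field.
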